#### **8.3.2.1.1. Definition of Adverse Events**

An AE is any untoward medical occurrence associated with the use of a drug in humans, whether or not considered drug related. Therefore an AE can be ANY unfavorable and unintended sign

(including an abnormal laboratory finding or vital sign measurement), symptom, or disease temporally associated with the use of a medicinal product, without any judgment about causality.

Events meeting the definition of an AE **include**:

- Exacerbation of a chronic or intermittent pre-existing condition including either an increase in frequency and/or intensity of the condition.
- New conditions detected or diagnosed after investigational product administration even though it may have been present prior to the start of the study.
- Signs, symptoms, or the clinical sequelae of a suspected drug interaction.
- Signs, symptoms, or the clinical sequelae of a suspected overdose of either investigational product or a concomitant medication.
- Clinically significant abnormal findings (laboratory test results, vital signs, physical examination findings, ECGs, radiologic exams or other studies) should be recorded as AEs. A “clinically significant” finding is one that affects clinical management, including additional visits, monitoring or referrals, diagnostic tests or alteration of treatment, or that is considered clinically significant by the investigator. A clinically significant finding may be a change in a test that has previously been abnormal but now requires additional action.
- When a medical or surgical procedure is performed, the condition that leads to the procedure should be recorded as the AE.

Events that **do not** meet the definition of an AE include:

- Anticipated day-to-day fluctuations or expected progression of pre-existing disease(s) or condition(s) present or detected at the start of the study unless judged by the investigator to be more severe than expected for the subject’s underlying condition.
- Abnormal laboratory, ECG, or vital sign measurements that are not labelled clinically significant (see definition above).
- Situations where an untoward medical occurrence did not occur (social and/or convenience admission to a hospital).
- Overdose in the absence of other AEs will not be reported as an AE in its own right.

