- Changes in C-SSRS during the course of the study indicating worsening should be evaluated by the investigator for clinical significance, and if clinically significant (e.g., alteration in medical care or intervention is required), an associated AE should be recorded, if present. The AE should be the primary underlying clinical manifestation assessed as clinically significant, and not the change in score itself.

Treatment emergent adverse events are defined as those that occur on or after the date of the first dose of double-blind investigational product.

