#### **11.1.5. Study Files and Retention of Records**

The investigator must maintain adequate and accurate records to enable the conduct of the study to be fully documented and the study data to be subsequently verified. These documents should be classified into at least the following 2 categories: (1) investigator's study file, and (2) subject clinical source documents.

The investigator's study file will contain the protocol/amendments, eCRF and query forms, IRB or IEC and governmental approval with correspondence, informed consent, drug records, staff curriculum vitae and authorization forms, and other appropriate documents and correspondence.

The required source data should include sequential notes containing at least the following information for each subject:

- Documentation that subject meets eligibility criteria, i.e., history, physical examination, and confirmation of diagnosis (to support inclusion and exclusion criteria);
- Participation in trial (including trial number);
- Trial discussed and date of informed consent;
- Dates of all visits;
- Documentation that protocol specific procedures were performed;

- Results of safety parameters, as required by the protocol;
- Start and end date of investigational product (including dose regimen, dispensing and return);
- Record of all AEs (start and end date, causality and intensity);
- Concomitant medication (including start and end dates, dose, and dose changes);
- Date of trial completion and reason for early discontinuation, if applicable.

All clinical study documents must be retained by the investigator until at least 2 years after the last approval of a marketing application in an ICH region (i.e., United States, Europe, or Japan) and until there are no pending or contemplated marketing applications in an ICH region; or, if no application is filed or if the application is not approved for such indication, until 10 years after the investigation is discontinued and regulatory authorities have been notified. Investigators may be required to retain documents longer if required by applicable regulatory requirements, by local regulations, or by an agreement with Axovant Sciences. The investigator must notify Axovant Sciences before destroying any clinical study records.

Should the investigator wish to assign the study records to another party or move them to another location, Axovant Sciences must be notified in writing in advance.

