4.1.5 Visits and Periods

There are 5 study periods during this study:

- The Screening Period is defined as the period of time prior to the subject receiving the first dose of single-blind placebo run-in medication.
- The Single-Blind Placebo Run-In Period (Period I) is defined as the period from the first dose of single-blind run-in medication and ends on the last dose date of single-blind run-in medication. The assessments taken on the date of the first dose of randomized double-blind investigational product will be assumed to have been completed before the first dose of double-blind investigational product and will be slotted to this period.
- The First Two-Week Double-Blind Treatment Period (Period II) starts on the date of first dose of double-blind investigational product and ends on the last dose date. If the first dose of randomized investigational product is taken on the same day as Visit 3 assessments, it will be assumed that the assessments were completed before the first dose of double-blind investigational product has been taken.
- The Single-Blind Placebo Washout Period (Period III) starts one day after the last dose of the double-blind medication has been taken in Period II and lasts until the first dose of the double-blind investigational product in Period IV. The assessments taken on the date of the first dose of randomized double-blind investigational product will be assumed to have been completed before the first dose of double-blind investigational product and will be slotted to this period.
- The Second Two-Week Double-Blind Treatment Period (Period IV) starts on the date of the first dose of double-blind investigational product and ends on the last dose date. If the first dose of randomized investigational product is taken on the same day as Visit 5 assessments, it will be assumed that the assessments were completed before the first dose of double-blind investigational product has been taken.

A safety follow-up telephone call will be conducted approximately 2 weeks after completion of Period IV.

Study visits will be determined from the scheduled times as reported on the CRF. As indicated in Table 1, Schedule of Assessments visit windows of +/- 3 days are allowed for scheduling purposes. For analysis purposes in this crossover study, no visit reassignment will be used even if a visit falls before or after the scheduling window.

Table 1: Schedule of Events

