7.1 Adverse Events

Adverse events will be classified using the MedDRA version 18.1 coding dictionary. Tabulations will include an overall incidence of at least one adverse event, incidence within system organ class (SOC), and incidence by preferred term. Each subject may only contribute once per treatment group, that is by first occurrence to each of the incidence rates, regardless of the number of occurrences, as follows:

- Adverse events occurring prior to the first dose of double-blind investigational product will be referred to as Treatment-Emergent AEs (TEAEs) and presented as Placebo Run-In events.
- Adverse events occurring on or after the first dose of each double-blind two-week treatment period (Period II and period IV), and within 7 days of the last dose of double-blind investigational product, will be referred to as TEAEs and presented by treatment group.
- Events occurring 7 days after the last dose of Period II and Period IV and for the post-treatment Follow-up Period starting at day 8 (up to 14 days post-last-dose) will be presented as Post-Treatment Period. These events will only be included in a data listing.

Tabulations of the incidence of AEs will be presented as follows:

- Overview of TEAE
- TEAE by SOC and preferred term
- TEAE by preferred term
- TEAE by SOC, preferred term, and relationship to study drug
- TEAE by SOC, preferred term, and maximum severity (mild, moderate, and severe)

All AEs will be listed with its relationship to study drug and severity, flagging those which are not events during treatment-emergent period.

A listing of all deaths and serious AEs will be provided. Any TEAE leading to study drug temporary and permanent discontinuation will also be listed.

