7.2 Clinical Laboratory

Clinical laboratory parameters will be presented using three methods:

1. Tabulations of observed values for the double-blind two-week periods pre-and post-treatment (Period II: Visit 3 and Visit 4; Period IV: Visit 5 and Visit 6) by treatment group.
2. Tabulations of the incidence of potentially clinically significant (PCS) values by treatment group. A focus will be on new-onset PCS values (ie, subjects with pre-existing PCS values at pre-treatment will not be considered to have new-onset values on-treatment). For purposes of this analysis, the most extreme (highest and lowest) value AT ANY TIME during Period II plus 7 days and Period IV plus 7 days for a parameter (for a given subject) will be used. Thus, a subject may contribute to both a low PCS value for a parameter as well as a high PCS value for that same parameter. PCS laboratory values are presented for serum chemistry in Table 2 and for hematology in Table 3.
3. Shifts from baseline to on-treatment, where values are categorized as low, normal, or high according to the lab normal values by treatment group. For purposes of this analysis, the most extreme on-treatment values will be used (most extreme low and most extreme high). On-Treatment values are considered values during Period II plus 7 days and during Period IV plus 7 days. Shifts from baseline will be based on laboratory normal ranges as provided by the central laboratory.

In addition, the incidence of TEAEs relating to hematology and serum chemistry laboratory parameters during Period II plus 7 days and Period IV plus 7 days will be presented by treatment group. These laboratory AEs will be identified from a review of the adverse events and select SOC and preferred terms will be included.

Table 2: Serum Chemistry Potentially Clinically Significant Criteria

Parameter	Gender	Low PCS	High PCS
Alanine aminotransferase (U/L)	Male	NA	133
	Female	NA	100
Albumin (g/L)	Male/Female	29	NA
Alkaline phosphatase (U/L)	Male	NA	323
	Female	NA	246
Aspartate aminotransferase (U/L)	Male	NA	118

	Female	NA	103
Direct bilirubin (umol/L)	Male/Female	NA	7.7
Total bilirubin (umol/L)	Male/Female	NA	30.8
Calcium (mmol/L)	Male/Female	1.99	2.91
Creatinine (umol/L)	Male	NA	174
	Female	NA	147
GGT (U/L)	Male	NA	136
	Female	NA	93
Creatinine clearance (mL/min)	Male/Female	59	NA
Random glucose (mmol/L)	Male/Female	2.9	NA
Potassium (mmol/L)	Male/Female	3.4	5.6
Sodium (mmol/L)	Male/Female	129	151

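### The SAP treats Visit 3 and Visit 5 tests as pre-dose, but has no matching rule for AEs found in them, so pre-treatment findings can be counted as TEAEs of the treatment that starts that day

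*SAP*

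**What the plan says.** **AE rules.** SAP 7.1 counts "Adverse events occurring on or after the first dose of each double-blind two-week treatment period (Period II and period IV), and within 7 days" (from the last dose) as TEAEs and shows them by treatment group. "Adverse events occurring prior to the first dose of double-blind investigational product" are shown as Placebo Run-In events. Events more than 7 days after the last dose of Period II or IV go to a listing only. Each subject counts once per treatment group, by first occurrence. Protocol 8.3.2.1.1 sets treatment emergence by date: "Treatment emergent adverse events are defined as those that occur on or after the date of the first dose of double-blind investigational product". SAP 4.3.1 requires a complete date to decide whether an AE was on treatment.

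**Laboratory TEAEs.** SAP 7.2 adds a table in which "the incidence of TEAEs relating to hematology and serum chemistry laboratory parameters during Period II plus 7 days and Period IV plus 7 days will" appear by treatment group. SAP 4.1.5 starts both periods on the date of the first double-blind dose.

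**Assessment rule.** For tests done on that date, SAP 4.1.5 says they "will be assumed to have been completed before the first dose of double-blind investigational product and will be slotted to this period", meaning run-in for Visit 3 and washout for Visit 5. SAP 4.1.2 makes them the period baselines.

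**Link between the two.** Protocol 8.3.2.1.1 states: "Clinically significant abnormal findings (laboratory test results, vital signs, physical examination findings, ECGs, radiologic exams or other studies) should be recorded as AEs".

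**The concern.** The plan recognises that Visit 3 and Visit 5 tests come before the dose and protects the laboratory, ECG and vital-sign tables accordingly. It does not carry that protection to the AE tables, although the same tests generate AEs. One abnormal result can then be a pre-treatment value in one table and an on-treatment event in another.

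Safety and tolerability is the secondary objective, and the by-treatment AE tables are its main output. Findings that predate a treatment would be added to both columns. That pulls the ratio between columns towards 1. Under the first-occurrence rule, a pre-dose event can also hide a later event of the same term that did arise on treatment.

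**Working it through.** The documents give no figure for this point, so there is nothing to reproduce. The check traces the rules, counts visits, and illustrates the size with assumed rates.

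**1. Tracing one result.** Take a clinically significant chemistry abnormality first found at Visit 5.
- Protocol Table 2 schedules chemistry, hematology, urinalysis, ECG, vital signs and examinations at Visits 3, 4, 5 and 6.
- Protocol 8.1 has the first tablet of the new period taken in clinic at Visits 3 and 5.
- Protocol 8.3.2.1.1 makes the abnormality an AE. Protocol 8.3.2.3 says the same of vital signs at any visit after Visit 1.
- Protocol 11.1.5 lists as AE source data "Record of all AEs (start and end date, causality and intensity", with no onset time.
- In the SAP 7.2 table of potentially clinically significant values, a qualifying result is pre-existing and so not new-onset. In the SAP 7.2 laboratory-TEAE table, the AE dated that day lies inside Period IV.

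At Visit 3 the same happens with Period II. The run-in label in SAP 7.1 does not keep such an event out of the laboratory-TEAE table, because SAP 7.1 calls run-in events TEAEs too.

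**2. Which column receives the pre-dose visit under the date rule**

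| Sequence | Visit 3 (pre-dose) | Visit 4 (end of treatment) | Visit 5 (pre-dose) | Visit 6 (end of treatment) |
|---|---|---|---|---|
| AB | intepirdine | intepirdine | placebo | placebo |
| BA | placebo | placebo | intepirdine | intepirdine |

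With 30–40 subjects, each column takes in 30–40 pre-dose and 30–40 end-of-treatment test visits. Half the scheduled test visits feeding each column are pre-dose.

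**3. Size, under assumed rates.** Let q be the background chance of a new clinically significant finding at a visit, equal at all visits, and d the intepirdine excess at its end-of-treatment visit. Onset is taken as the test date.
- Correct assignment, expected events per subject: q + d against q, a ratio of 1 + d/q.
- Date rule: q + (q + d) = 2q + d against 2q, a ratio of 1 + d/(2q).
- For d = q, 2.0 becomes 1.5. For d = 2q, 3.0 becomes 2.0. Neither depends on q. The expected difference in event counts stays at d.

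If each subject is counted once and visits are independent, the incidences are 1 − (1 − q)(1 − q − d) and 1 − (1 − q)². Their difference is (1 − q)d, so it shrinks by the fraction q. For d = q:

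| q | True incidence | Date-rule incidence | Difference: true → date rule | Pre-dose findings added per column (30–40 × q) |
|---|---|---|---|---|
| 0.02 | 4% vs 2% | 5.92% vs 3.96% | 2 → 1.96 points | 0.6–0.8 |
| 0.05 | 10% vs 5% | 14.5% vs 9.75% | 5 → 4.75 points | 1.5–2 |
| 0.10 | 20% vs 10% | 28% vs 19% | 10 → 9 points | 3–4 |

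**4. Where an AB Visit 5 finding belongs.** Visit 5 follows Visit 4 by 14 ± 3 days, that is 11–17. The last intepirdine dose falls on the day of Visit 4 or the day before, so Visit 5 is 11–18 days after it. That is 11 − 7 = 4 to 18 − 7 = 11 days beyond the 7-day window. Under the SAP's own rule the finding is a washout or post-treatment event.

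**The case against.** SAP 7.1 refers to the first dose, not its date, and SAP 4.2 gives the SAP precedence over the protocol. Read with SAP 4.1.5, a Visit 3 finding is before the dose and goes to run-in. A Visit 5 finding is outside both treatment windows and goes to the listing. Protocol 10.4.1.1 assigns AEs by the last dose received, which for these findings is run-in or washout placebo. Protocol 7.6 records the time of in-clinic doses, and the AE items in Protocol 11.1.5 are a minimum, so onset time might exist. No section says that the test date is the onset date. The safety analysis is descriptive, and all AEs are listed.

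Much of this stands. The defect is a missing tie-break, not an explicit wrong rule, and the sections can be read consistently. Protocol 8.3.2.1.1 also settles only whether an event is treatment-emergent, not which treatment it belongs to. But the consistent reading is not written down. A dose time helps only if there is an AE time to compare with it, and none is listed. The laboratory-TEAE table is defined by periods that start on a date, so the literal wording of SAP 7.1 does not protect it. The last-dose rule is not carried into the SAP.

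A reader might go further and infer that misassignment runs one way, moving late intepirdine events to placebo in sequence AB. The documents do not support that. By step 4, such an event would not be in the intepirdine column anyway; the error is placebo instead of washout. Background findings are misplaced in both directions. Nor do the documents give a half-life or delayed-effect data that would justify a rate of late intepirdine findings at Visit 5, so any further loss in the risk ratio built on such a rate has no basis.

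**Conclusion.** The point holds as a gap in the rules. Ordinary date-based programming would place clinically significant findings from the pre-dose Visit 3 and Visit 5 tests in the TEAE column of a treatment not yet taken, against the SAP's own baseline rule. Both columns gain pre-treatment findings: AB gives Visit 3 to intepirdine and Visit 5 to placebo, and BA the reverse.

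Among visit-detected AEs the ratio is diluted (2.0 to about 1.5 under the equal-rate assumption). The difference in incidence shrinks only by the fraction q. These figures rest on the date rule being applied, onset equal to test date, equal q at each visit and, for incidence, independence between visits. Symptom AEs with onset on other days and the laboratory, ECG and vital-sign tables are unaffected. Absolute numbers are probably small, but the correction is cheap and should be made before database lock.

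**What to change.** Add to SAP 7.1, and apply in the SAP 7.2 laboratory-TEAE table: *An AE arising from a laboratory, ECG, vital-sign or examination assessment done on the first-dose date of Period II or Period IV is assigned to the period to which Section 4.1.5 slots that assessment (Placebo Run-In for Visit 3, Washout for Visit 5), and is not a TEAE of the treatment starting that day, unless the assessment is documented as post-dose.* Other AEs with onset that day stay under the current rule and are flagged in the listing.

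Show the reassigned Visit 5 events in a washout summary by preceding treatment. Otherwise SAP 7.1 would leave them in a listing only, where a delayed effect could be missed. Reconcile Protocol 8.3.2.1.1 and 10.4.1.1 with SAP 4.1.5, 7, 7.1 and 7.2.

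The cost is one sentence, one small table, and a blinded pre-lock check of AEs dated to Visit 3 or Visit 5 in 30–40 subjects. A post-dose finding not documented as such would move to the earlier period, which SAP 4.1.5 already assumes for the assessment itself.

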7.2 Clinical Laboratory

Clinical laboratory parameters will be presented using three methods:

1. Tabulations of observed values for the double-blind two-week periods pre-and post-treatment (Period II: Visit 3 and Visit 4; Period IV: Visit 5 and Visit 6) by treatment group.
2. Tabulations of the incidence of potentially clinically significant (PCS) values by treatment group. A focus will be on new-onset PCS values (ie, subjects with pre-existing PCS values at pre-treatment will not be considered to have new-onset values on-treatment). For purposes of this analysis, the most extreme (highest and lowest) value AT ANY TIME during Period II plus 7 days and Period IV plus 7 days for a parameter (for a given subject) will be used. Thus, a subject may contribute to both a low PCS value for a parameter as well as a high PCS value for that same parameter. PCS laboratory values are presented for serum chemistry in Table 2 and for hematology in Table 3.
3. Shifts from baseline to on-treatment, where values are categorized as low, normal, or high according to the lab normal values by treatment group. For purposes of this analysis, the most extreme on-treatment values will be used (most extreme low and most extreme high). On-Treatment values are considered values during Period II plus 7 days and during Period IV plus 7 days. Shifts from baseline will be based on laboratory normal ranges as provided by the central laboratory.

In addition, the incidence of TEAEs relating to hematology and serum chemistry laboratory parameters during Period II plus 7 days and Period IV plus 7 days will be presented by treatment group. These laboratory AEs will be identified from a review of the adverse events and select SOC and preferred terms will be included.

Table 2: Serum Chemistry Potentially Clinically Significant Criteria

Parameter	Gender	Low PCS	High PCS
Alanine aminotransferase (U/L)	Male	NA	133
	Female	NA	100
Albumin (g/L)	Male/Female	29	NA
Alkaline phosphatase (U/L)	Male	NA	323
	Female	NA	246
Aspartate aminotransferase (U/L)	Male	NA	118

	Female	NA	103
Direct bilirubin (umol/L)	Male/Female	NA	7.7
Total bilirubin (umol/L)	Male/Female	NA	30.8
Calcium (mmol/L)	Male/Female	1.99	2.91
Creatinine (umol/L)	Male	NA	174
	Female	NA	147
GGT (U/L)	Male	NA	136
	Female	NA	93
Creatinine clearance (mL/min)	Male/Female	59	NA
Random glucose (mmol/L)	Male/Female	2.9	NA
Potassium (mmol/L)	Male/Female	3.4	5.6
Sodium (mmol/L)	Male/Female	129	151

Table 3: Hematology and Differentials Potentially Clinically Significant Criteria

Parameter	Gender	Low PCS	High PCS
WBC ($10^9/L$)	Male/Female	2.9	100.1
Hemoglobin (g/L)	Male	99	196
	Female	99	181
Platelets ($10^9/L$)	Male/Female	74	NA
Absolute neutrophil count ($10^9/L$)	Male/Female	1.4	NA
Calculated absolute neutrophil count ($10^9/L$)	Male/Female	1.4	NA
Absolute lymphocyte count ($10^9/L$)	Male/Female	0.7	5.1
Calculated absolute lymphocyte count ($10^9/L$)	Male/Female	0.7	4.1

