### 6.2. Inclusion Criteria

Subjects eligible for enrollment in the study must meet all of the following criteria:

1. Male or female subject with a clinical diagnosis of probable Alzheimer's disease (AD), probable dementia with Lewy bodies (DLB), or probable Parkinson's disease dementia (PDD). The diagnosis of probable AD must be in accordance with the recommendations from the National Institute on Aging-Alzheimer's Association workgroups on diagnostic guidelines for AD (McKhann et al., 2011). The diagnosis of probable DLB must be in accordance with Consensus criteria for DLB diagnosis (McKeith et al., 2005). The diagnosis of probable PDD must be in accordance with the Movement Disorder Society (MDS) criteria for PDD (Emre et al., 2007).
2. Subject has an MMSE score of 14 to 26 inclusive and able to follow instructions at the Screening Visit.
3. Subject must have experienced at least one fall within the past two years as assessed by history and defined by the judgment of the clinical investigator at the time of the Screening Visit.
4. Clinically relevant risk of fall. For example, patients have an average gait speed of less than 100 cm/s on an electronic walkway evaluation at Visit 1, Visit 2 and Visit 3 or abnormal gait and balance on the miniBEST assessment with a score < 16 at Visit 1-3. In case these criteria are not met, a justification for the clinically determined fall risk should be documented and discussed with the medical monitor. Other documented risks of fall or gait impairment may be acceptable with approval from the medical monitor. Mandatory need for a walking aid could for example be considered as such a condition.
5. Subject has a Hachinski Ischemia score less than or equal to 4 at Screening.
6. Subject has a documented history of at least 6 weeks of stable cholinesterase inhibitor therapy prior to screening, with no intent to change for the duration of the study.
7. Age 50 to 89 years, inclusive, at the time of the Screening Visit.
8. Female subjects must be:
  - a. Of non-childbearing potential (i.e., any female who is post-menopausal [greater than 1 year without menstrual period in the absence of hormone replacement therapy]) or surgically sterile; or,

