7 SAFETY SUMMARIES AND ANALYSES

The safety analysis will be descriptive in nature, and will be presented for the Safety Population. All safety data collected and captured in the CRF will be included in data listings sorted by domain, sequence, subject, and time point, or as appropriate. Mean changes from pre-treatment to on-treatment (Periods II and IV together) will be tabulated by treatment, while the number of subjects with potentially clinically significant values at pre-treatment and at the end of each double-blind two-week treatment period (Period II and Period IV) will be presented.

Generally, safety data will be presented for the Placebo Run-In Period, for the Double-Blind Treatment Period by treatment group (Period II and Period IV plus 7 days after the end of these periods, for the Washout Period starting at day 8 of the Washout Period, and for the post-treatment Follow-up Period starting at day 8 of the Follow-up Period.

All safety data will be summarized overall and then by stratified subgroup: dementia type (AD, LBD) and baseline MMSE (14-19 and 20-26).

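### The creatinine-clearance criterion in SAP Table 2 has no change-from-baseline term, so the new-onset table cannot show worsening in subjects already below 59 mL/min

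*SAP*

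**What the plan says.** SAP 7.2, Table 2, sets the criterion as "Creatinine clearance (mL/min) Male/Female 59 NA": one low limit for both sexes, no high limit and no change term. The table prints no operator, so it does not say whether a value of exactly 59 counts.

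The planned output is "Tabulations of the incidence of potentially clinically significant (PCS) values by treatment group. A focus will be on new-onset PCS values", and the new-onset rule is that "subjects with pre-existing PCS values at pre-treatment will not be considered to have new-onset values on-treatment". SAP 4.1.2 defines baseline by period: Visit 3 for Period II and Visit 5 for Period IV.

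Other planned outputs also bear on the point:

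- SAP 7 presents "the number of subjects with potentially clinically significant values at pre-treatment and at the end of each double-blind two-week treatment period".
- SAP 7 also states that "Mean changes from pre-treatment to on-treatment (Periods II and IV together) will be tabulated by treatment", and it lists all safety data.
- SAP 7.2 plans a shift table: "Shifts from baseline to on-treatment, where values are categorized as low, normal, or high according to the lab normal values by treatment group".
- SAP Table 2 gives serum creatinine its own high limits, 174 umol/L for men and 147 umol/L for women.

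On entry, Protocol 6.2 allows "Age 50 to 89 years, inclusive, at the time of the Screening Visit". Protocol 6.3 excludes progressive kidney dysfunction (criterion 10) and creatinine above 1.5 mg/dl when judged clinically significant (criterion 23). It sets no limit on clearance. Protocol Table 3 lists creatinine but not clearance, and neither document names a formula for it.

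**The concern.** Clearance declines with age, so in a sample aged 50 to 89 some subjects can be expected to start below 59 mL/min. An absolute limit combined with a new-onset rule puts these subjects outside the table that the SAP emphasises. They have the least renal reserve, and a further fall in them is what a renal safety summary should show.

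The shift table does not help, because a subject already in the low category stays there. Safety and tolerability is the trial's only secondary objective. With 30 to 40 subjects, a handful of individual declines is the most that a renal signal could consist of.

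**Working it through.** No sample-size, power or error-rate figure is involved, and 59 mL/min is a set threshold with no derivation to reproduce. The check applies the rule to example values, tests the creatinine row as a backstop, and then sizes the affected group under stated assumptions.

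**1. The rule.** New-onset means PCS on treatment and not PCS at that period's pre-treatment assessment. The example values are illustrative.

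| Clearance before → on treatment | Fall | New-onset if limit is ≤59 | New-onset if limit is <59 |
|---|---|---|---|
| 60 → 59 | 1.7% | yes | no |
| 59 → 30 | 49.2% | no | yes |
| 58 → 29 | 50.0% | no | no |
| 55 → 25 | 54.5% | no | no |
| 45 → 20 | 55.6% | no | no |
| 120 → 60 | 50.0% | no | no |

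The operator changes only the rows that involve exactly 59. Under either reading, a subject who starts below the limit is PCS both before and on treatment and is never new-onset. The last row shows that halving from a high value is not flagged either.

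**2. Serum creatinine as a backstop.** Assume that clearance varies as 1/creatinine at fixed age and weight. The fall in clearance needed to reach the creatinine limit is then 1 − (baseline creatinine ÷ limit).

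- Men, limit 174: baseline 70 needs 1 − 70/174 = 59.8%; 90 needs 48.3%; 110 needs 36.8%; 132.6 (1.5 mg/dl × 88.4) needs 23.8%.
- Women, limit 147: baseline 70 needs 52.4%; 90 needs 38.8%; 110 needs 25.2%; 132.6 needs 9.8%.

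Conversely, the row catches a fall of fraction d only if baseline creatinine is at least limit × (1 − d):

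| Fall | Men: baseline at least | Women: baseline at least |
|---|---|---|
| 25% | 174 × 0.75 = 130.5 | 147 × 0.75 = 110.3 |
| 40% | 174 × 0.60 = 104.4 | 147 × 0.60 = 88.2 |
| 45% | 174 × 0.55 = 95.7 | 147 × 0.55 = 80.9 |

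In older or lighter subjects clearance can be below 59 at creatinine values under these thresholds. Take Cockcroft-Gault (an assumed formula), age 75 and weight 75 kg. Clearance is 59 at (140 − 75) × 75 ÷ (72 × 59) × 88.4 ≈ 101 umol/L in a man, and at 0.85 times that, about 86, in a woman. At age 80 and 60 kg the values are about 75 and 64.

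**3. Size of the group.** These inputs are assumptions and none comes from the documents: Cockcroft-Gault; mean age 70 to 78 (SD 7, limited to 50–89); 45% women; mean weight 80 kg (men) and 68 kg (women), SD 12 to 15 kg; mean creatinine 88 and 72 umol/L with 18% spread. Simulation gives:

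- Share starting at or below 59: roughly 20% to 35%. That is 0.20 × 30 = 6 to 0.35 × 40 = 14 subjects.
- Among them, share of falls caught by the creatinine row: about 2% to 4% of 25% falls, 28% to 39% of 40% falls, and roughly half of 45% falls.

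**The case against.** The strongest reply is that the renal data are summarised in several other ways.

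- New onset is a focus, not the whole output. Overall PCS incidence, counts before and at the end of each period, mean changes and listings are all planned. Protocol 10.4.1.2 also calls for change from baseline in each quantitative laboratory value by treatment.
- The adverse-event definition in Protocol 8.3.2.1.1 covers a change in a previously abnormal test that now needs action. SAP 7.2 reports laboratory-related adverse events by treatment.
- Large falls often reach the creatinine row.
- Every row of Tables 2 and 3 is an absolute limit under the same rule. The laboratory analysis is descriptive, so no test result changes.

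All of this stands as far as it goes. It rules out two stronger readings. A reader might infer that renal safety is reported as new onset only, but the SAP plans the other outputs too. A reader might also infer that no fall in these subjects can ever be flagged. That holds only for the new-onset clearance flag, and only within a period: a subject below 59 at Visit 3 but above it at Visit 5 can be new-onset in Period IV. Nor can it be said outright that a change from 60 to 59 is flagged, since that requires the limit to mean ≤59, which Table 2 does not state.

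The other outputs still do not count individual declines in clearance by treatment. Overall PCS incidence and the before/end counts record the same subject as PCS at both times, means dilute individual falls, listings are not a summary, and adverse-event recording depends on the investigator's judgement.

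**Conclusion.** The point holds as a limited gap. The new-onset tabulation on which SAP 7.2 focuses cannot identify worsening clearance in subjects already below the limit at that period's pre-treatment assessment, and no planned by-treatment table counts their individual declines. This follows from the text alone, under either reading of the operator.

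The size rests entirely on the assumed inputs: roughly 6 to 14 subjects would be affected, and the creatinine row would miss nearly all 25% falls and about half of 45% falls among them. Different weights, creatinine levels or formula would move these figures, and the kidney-related exclusions may remove some subjects likely to decline.

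The same structure applies to the other rows of Tables 2 and 3. Clearance is singled out because, at these ages, its baseline values are likely to be low already. No efficacy conclusion or hypothesis test is affected. This is an inexpensive improvement, not an error that threatens the trial.

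**What to change.** Keep the absolute row in SAP Table 2 and add a descriptive row, by treatment: *creatinine clearance decrease of at least 25% from the period baseline (Visit 3 or Visit 5), counted whatever the baseline value*. In the examples above, this row counts 59 → 30, 55 → 25, 45 → 20 and 120 → 60, and does not count 60 → 59. When adding it, name the clearance formula and its inputs, and state whether the limit is <59 or ≤59.

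The form is already in use in the SAP: Table 4 defines weight criteria purely as a percentage change, and Table 5 has a stand-alone row for increase in QTcF.

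The cost is one more derived variable and one more table row. The percentage is a reporting convention, and 20% or 30% would also serve. It should be fixed before unblinding.
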